Have received an FDA authorized booster dose of mRNA (BNT162b2 or mRNA 1273) vaccine at least 28 days before study enrollment

Exclusion Criteria

Patients who have had a serious adverse reaction to any prior COVID-19 vaccines resulting in emergency room visit or hospitalization, had events related to myocarditis, thrombosis and thrombocytopenia syndrome or anaphylaxis to any prior dose of the COVID-19 vaccines.

Patients who have had a documented COVID-19 infection in the 90 days prior to study enrollment

Outcomes

Primary outcome: Rates of seroconversion for SARS-CoV-2 spike antibody after 4 weeks following an additional booster dose of BNT162b2/AdCov2.S COVID vaccine in patients that had a poor serological response after standard vaccine series (allowing additional booster dose)

Secondary outcomes: Safety of booster dose of BNT162b2 and AdCov2.S vaccines, correlation between malignancy type and prior treatment type and seroconversion, correlation between timing of most recent cancer-directed treatment and seroconversion, correlation between the total number of cancer-directed treatments received and seroconversion, differences between booster efficacy dependent on prior vaccine type (BNT162b2 versus mRNA-1273), T cell responses at baseline and 4 weeks following vaccination, Antigen neutralization assay results at baseline and 4 weeks following vaccination, duration of sustained immunogenicity following vaccination in seropositive patients, correlations with baseline immune status correlates such as lymphocyte subsets/immune globulin levels

Safety monitoring.

Patients who have met all eligibility criteria will then be randomized 1:1 to receive either the BNT162b2 or AdCov2.S and then will be scheduled to receive their study dose at the Montefiore Vaccine Center. Each patient will be observed for a minimum of 15 minutes after their vaccination to monitor for any adverse

effects in the Montefiore Vaccine Center as per the Vaccine Center protocol.

Cohort 3

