On December 16, 2021 the CDC published updated recommendations regarding use of the Ad26.COV2.S (Johnson & Johnson) vaccine (<https://www.cdc.gov/media/releases/2021/s1216-covid-19-vaccines.html>) due to the rare but persistent adverse event thrombosis with thrombocytopenia syndrome (TTS) seen with the Ad26.COV2.S vaccine alone. They expressed a clinical preference for individuals to receive an mRNA COVID-19 vaccine over an Ad26.COV2.S vaccine, however, reaffirmed that receiving any vaccine is better than being unvaccinated. This recommendation, however, did not specify stipulations for our currently immunosuppressed patients with cancer population who have already received three prior mRNA COVID-19 vaccines with minimal or no response. Given our patient population remains at high-risk for severe COVID-19 despite three prior mRNA COVID-19 vaccines, we feel the administration and efficacy evaluation of Ad26.COV2.S (Johnson & Johnson) vaccine as a mix and match strategy for booster vaccination continues to remain warranted as part of our study. In fact, a recent study from South Africa does suggest excellent efficacy of a booster Ad26.COV2.S vaccine corroborating this approach¹⁵.

Some patients, however, remain hesitant to receive an Ad26.COV2.S given its rare but potentially severe adverse event as outlined above. Thereby, for study candidates who prefer not be randomized in cohort 2, participation in cohort 3 will be offered. Cohort 3 will be a prospective, non-randomized cohort to address the question of whether a switch mRNA vaccine approach might be more effective at achieving an increased immune response in poor responders to a prior series of three mRNA vaccinations (mRNA-1273 (Moderna) or BNT162b2 (Pfizer/BioNTech)). Eligible patients will be prospectively followed to receive a BNT162b2 vaccine as a fourth dose evaluating their increase in mean SARS-CoV-2 Spike IgG titers above a pre-established threshold by 4 weeks following vaccination as the primary endpoint with further secondary endpoints regarding safety, neutralization antibody and T cell assays and durability of response with assessments at 3, 6, 12 and 24 months. As it is anticipated that about 60-70% of study candidates will have previously received BNT162b2 and 30-40% mRNA-1273, this cohort will allow an assessment of a switch approach in a non-randomized single arm fashion.

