Our proposed study is a prospective single arm study, which will aim in an exploratory/pilot fashion to assess the following variables in a population of patients with cancer with prior vaccination against COVID-19.

- To study the difference in mean titers for SARS-CoV-2 spike IgG in patients with cancer after administering an additional (fourth) booster dose of the BNT162b2 vaccine in patients that had a poor serological response after standard homologous (BNT162b2 → BNT162b2) vs. heterologous (mRNA-1273 → BNT162b2) vaccine series (including a third dose).
- To study safety and side effects from an additional booster dose of the BNT162b2 COVID vaccine

Inclusion criteria:

Our target population consists of patients with a known or previous diagnosis of cancer who had received three prior doses of one of the mRNA based COVID-19 vaccines including a booster dose. Our study will employ the following inclusion criteria:

- Above the age of 18
- Have a diagnosis of prior or active malignancy- either hematological or solid tumor
- Have a negative or low-level SARS-CoV-2 spike IgG after at least 14 days of booster vaccination series irrespective of active/inactive cancer status, on observation, or active therapy.
- Have received an FDA authorized booster dose of mRNA (BNT162b2 or mRNA 1273) vaccine at least 28 days before study enrollment

- Decline to participate in cohort 2 requiring randomization of BNT162b2 and Ad26.CoV2.S vaccines

Exclusion Criteria

- Patients who have had a serious adverse reaction to any prior COVID-19 vaccines resulting in emergency room visit or hospitalization, had events related to myocarditis, thrombosis and thrombocytopenia syndrome or anaphylaxis to any prior dose of the COVID-19 vaccines.
- Patients who have had a documented COVID-19 infection in the 90 days prior to study enrollment

Outcomes

Primary outcome: To compare the increase in mean titers for SARS-CoV-2 spike antibody after 4 weeks following a homologous (BNT162b2 → BNT162b2) vs. heterologous (mRNA-1273 → BNT162b2) additional booster dose of COVID vaccine in patients that had a poor serological response after standard vaccine series (including a third dose).

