Secondary outcomes: Safety of additional booster dose of BNT162b2 vaccine, correlation between malignancy type and prior treatment type and change in mean titer, correlation between timing of most recent cancer-directed treatment and change in mean titer, correlation between the total number of cancer-directed treatments received and change in mean titer, T cell responses at baseline and 4 weeks following vaccination, Antigen neutralization assay results at baseline and 4 weeks following vaccination, duration of sustained immunogenicity following vaccination in seropositive patients, correlations with baseline immune status correlates such as lymphocyte subsets/immune globulin levels

Safety monitoring

Patients who have met all eligibility criteria as part of cohort 3 will receive the BNT162b2 vaccine study dose at the Montefiore Vaccine Center. Each patient will be observed for a minimum of 15 minutes after their vaccination to monitor for any adverse effects in the Montefiore Vaccine Center as per the Vaccine Center protocol.

Methods

We will employ several methods for patient identification/recruitment.

- Using EPIC EMR and Montefiore Einstein Cancer-Center's Quality 360 team, we will identify patients that have undergone SARS-CoV-2 spike antibody testing. Patients with a test will then be checked if they have completed the full vaccination series for one of the FDA's Emergency Use Authorized COVID vaccines (i.e. 2 doses of the mRNA-based mRNA- 1273 (Moderna) or BNT162b2 (Pfizer/BioNTech) or a single dose of the adenovirus- based Ad26.COV2.S (Johnson & Johnson) vaccine and at least 14 days have passed since the second dose of the mRNA-based vaccines (Moderna or Pfizer/BioNTech) or 28 days have passed since the adenovirus-based Johnson & Johnson vaccine. If patients meet the above criteria, they will be offered participation in our study.

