Cohort 1. For a 1 sample test of proportions our hypothesis is that booster vaccine dosing will induce detectable immunity by the spike IgG assay in at least 20% of individuals. Null hypothesis is a positivity rate of 10% to account for some test variability and therefore the alternative hypothesis is $p > 30\%$. Our planned sample size of up to 250 will have ample power ($>95\%$) to detect such a difference in our primary endpoint and will still retain 80% power and 5% significance in the secondary preplanned subset analyses as long as cohort sizes per subset are >26 . We anticipate the large majority of patients will be hematologic malignancy patients and such preplanned subset analyses will include two cohorts, the highly immune suppressed (prior anti- CD20, CAR-T, or SCT therapy), and all others (solid tumor/hematologic malignancy patients) who do not fall into the first cohort. We anticipate cohort sizes of at least 26 per cohort based on the numbers of seronegative patients identified in our prior study.

Cohort 2. Our null hypothesis is that the additional homologous booster vaccine dosing will induce detectable immunity (positive spike IgG test result higher than the predefined threshold for seropositivity—i.e. >1000 AU/ml) by the spike IgG assay in at least 25% of individuals. Alternate hypothesis is that heterologous vaccination with the AdCov2.S vaccine will increase this seroconversion rate by an additional 25%- that is to 50%. With an alpha of 0.05 and 80% power to detect the difference, we would require a sample size of 46 in each group. Accounting for 5% dropout rate, we will thus use a planned sample size of up to 100 subjects. We anticipate the large majority of patients will be hematologic malignancy patients and such preplanned subset analyses will include two cohorts, the highly immune suppressed (prior anti-CD20, CAR-T, or SCT therapy), and all others (solid tumor/hematologic malignancy patients) who do not fall into the first cohort.

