Patients would serve as their own control. Baseline seropositivity rate by definition is 0% for the cohort but anticipating natural and laboratory variation we have based on statistical null hypothesis around a 10% seropositivity rate at 4 weeks and anticipate that booster vaccination will increase this to higher than 30%.

Planned intervention

Cohort 1

The planned intervention is to administer a booster dose of the BNT162b2 (Pfizer/BioNTech) or mRNA-1273 (Moderna) vaccine to patients that meet FDA/CDC criteria of cancer on active therapy or patients that have received a stem cell transplantation or CAR-T cell therapy in the last 2 years or those that have a negative spike IgG after having = completed one of the FDA's Emergency Use Authorized vaccination series for COVID-19 (i.e. 2 doses of the mRNA-based mRNA-1273 (Moderna), BNT162b2 (Pfizer/BioNTech), or a single dose of the adenovirus-based Ad26.COV2.S (Johnson & Johnson) vaccine, following completion of their vaccination series.

Cohort 2

The planned intervention is to administer an additional booster dose of the BNT162b2 (Pfizer/BioNTech) or Ad26.COV2.S (Johnson & Johnson) vaccine to patients that meet eligibility criteria for cohort 2 in a 1:1 randomization fashion with negative spike antibody vs. low positive antibody level serving as a stratification factor to ensure controlling for key confounder.

Cohort 3

The planned intervention is to administer an additional booster dose of the BNT162b2 (Pfizer/BioNTech) vaccine to patients that meet eligibility criteria for cohort 3 in a prospective single arm fashion in patients that had a poor serological response after standard vaccine series (including a third dose).

Participant recruitment

The study will both utilize data from the electronic health record to identify patients meeting the above inclusion criteria and enroll them on to the study and accept patients self-referred or referred by their provider at Montefiore Medical Center or external institutions. A consenting visit will be scheduled with each prospective patient. Following a carefully conducted and documented informed consent process subjects who consent for study participation will then be screened. Patients who qualify for booster COVID-19 vaccination as per FDA/CDC guidance and study criteria will then participate in our study.

Data and Safety Monitoring Plan

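### Cohort 2 is randomised before the vaccine visit is scheduled, and nothing plans for refusal after allocation or closes cohort 3 to patients already randomised

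*Combined protocol and SAP*

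**What the plan says.** The Safety monitoring paragraph for cohort 2 sets the order of events: "Patients who have met all eligibility criteria will then be randomized 1:1 to receive either the BNT162b2 or AdCov2.S and then will be scheduled". The cohort 2 study calendar has separate columns for screening, the initial visit and the vaccine day (D0). It does not show when randomisation takes place, and no interval between allocation and dose is given. Under Planned intervention, allocation is described as a "1:1 randomization fashion with negative spike antibody vs. low positive antibody level serving as a stratification factor". Neither blinding nor a placebo is described for this comparison.

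The cohort 3 rationale explains why a non-randomised cohort was added: "Some patients, however, remain hesitant to receive an Ad26.COV2.S given its rare but potentially severe adverse event as outlined above". It continues that "for study candidates who prefer not be randomized in cohort 2, participation in cohort 3 will be offered". The matching cohort 3 inclusion criterion is worded differently: "Decline to participate in cohort 2 requiring randomization of BNT162b2 and Ad26.CoV2.S vaccines". It has no time point, and neither the inclusion nor the exclusion list mentions patients already allocated in cohort 2. Everyone in cohort 3 gets the same vaccine: "Patients who have met all eligibility criteria as part of cohort 3 will receive the BNT162b2 vaccine study dose".

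The Sample size section plans 46 per group for cohort 2 (25% against 50%, alpha 0.05, 80% power) and up to 100 in total, "Accounting for 5% dropout rate". That rate is not split by arm. The Statistical analysis section defines no analysis population and gives no rule for a patient who is randomised but not dosed as allocated.

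**The concern.** A gap between allocation and dosing is harmless when patients do not know their arm or do not mind which one they get. Here the first condition is not secured, and the protocol says the second fails for some patients. A patient may consent, be allocated Ad26.COV2.S and then change their mind before the vaccine visit. Cohort 3 offers BNT162b2 within the same study, and a site reading its criterion literally could count that patient as having declined cohort 2.

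Cohort 2 is the study's only randomised comparison, with about 50 patients per arm. Loss concentrated in one arm does one of two things. If refusers stay in the analysis, the contrast is diluted. If they are dropped, the Ad26.COV2.S arm becomes a selected group set against an unselected one. With no analysis set defined, that choice could be made after the results are known. Patients who moved would also enter the cohort 3 comparison of prior BNT162b2 with prior mRNA-1273, having been selected by their cohort 2 allocation.

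**Working it through.** **Inputs from the Sample size section.** Response 25% on BNT162b2 and 50% on Ad26.COV2.S; alpha 0.05 with sidedness not stated; power 80%; 46 per group; 5% dropout; up to 100 in total, so 50 per arm at 1:1.

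**Reproducing the plan's figure.** Pooled-variance formula for two proportions, with mean rate p̄ = 0.375:

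n = [z(1−α)·√(2p̄(1−p̄)) + z(0.80)·√(p1(1−p1) + p2(1−p2))]² / (p2−p1)²

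- One-sided 5%: [1.645·√0.46875 + 0.842·√0.4375]² / 0.0625 = 45.3, so 46. This matches.
- Two-sided 5%: 58. This does not match.

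The one-sided setting is therefore used below. Power is 80.5% at 46 per arm and 83.4% at 50. For dropout, 92/0.95 = 96.8, so 97, rounded up in the plan to 100. Fifty per arm can lose 4 patients (8%) before falling below 46.

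**Assumption.** The documents give no refusal rate, so r = 5%, 10% and 20% is taken as a range, in the Ad26.COV2.S arm only, with no other dropout.

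**Effect on the Ad26.COV2.S response rate**

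- (a) Refusers kept in their arm as non-responders: p2 = 0.50(1−r).
- (b) Refusers take BNT162b2, respond at 25%, and are analysed as randomised: p2 = 0.50(1−r) + 0.25r.
- (c) Refusers excluded: p2 stays at 0.50, with 50(1−r) patients in that arm.

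Power = Φ{[(p2−0.25) − 1.645·SE0] / SE1}, where SE0 is the pooled and SE1 the unpooled standard error. Example for (a) at r = 10%: p2 = 0.45, SE0 = 0.0954, SE1 = 0.0933, so (0.200 − 0.157)/0.0933 = 0.46 and power is 67.8%.

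| Refusal r (patients of 50) | (a) p2, power | (b) p2, power | (c) power |
|---|---|---|---|
| 0 | 50%, 83.4% | 50%, 83.4% | 83.4% |
| 5% (2.5) | 47.5%, 76.3% | 48.75%, 80.0% | 82.6% |
| 10% (5) | 45%, 67.8% | 47.5%, 76.3% | 81.6% |
| 20% (10) | 40%, 48.2% | 45%, 67.8% | 79.5% |

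**Bias under (c).** Suppose there is no true difference, with 25% in both arms, and 20% of the Ad26.COV2.S arm is excluded. If those refusers would have responded at rate q, the remaining patients respond at (0.25 − 0.20q)/0.80. With q = 0 this is 31.25%, and with q = 50% it is 18.75%: a spurious shift of 6.25 points in either direction.

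**The case against.** The protocol has already dealt with the most obvious source of refusal. Anyone who wants to be sure of BNT162b2 can choose cohort 3 at the outset, so those who accept cohort 2 have been filtered for willingness to take Ad26.COV2.S, and later refusal may be rare. This stands: it limits how high r is likely to be, and it is why the table illustrates and does not forecast.

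The direction is not certain either. Cohort 2 patients have responded poorly to three mRNA doses, and some may join in the hope of the switch and lose interest when allocated BNT162b2. That is plausible, but the protocol records hesitancy only towards Ad26.COV2.S, and cohort 3 provides an alternative only for patients leaving that arm.

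A reader might infer that the protocol permits crossing into cohort 3. It does not say so. The rationale speaks of candidates who prefer not to be randomised, which describes a choice before allocation. The criterion merely fails to exclude the later case. A reader might also infer that the trial is declared open-label, or that patients wait days between allocation and dose. The first is a reasonable inference from the absence of any blinding text; the second has no support, since no interval is stated.

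Finally, cohort 2 is described as exploratory and its endpoint is a laboratory titer. That lowers the stakes but does not protect the comparison.

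**Conclusion.** The point holds as an avoidable weakness in the sequence and an unclosed gap in the wording. The stated order lets patients learn their arm before dosing. Refusal after allocation is not planned for, and would probably fall more on Ad26.COV2.S. Cohort 3 is not closed to patients already randomised.

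On the assumed range of 5% to 20% refusal in that arm, power falls from 83% to between 76% and 48% with refusers as non-responders, or to between 80% and 68% if they take BNT162b2 and are analysed as randomised. Exclusion costs little power but can move the estimate by about 6 points at 20%, if refusers' response differs as much as assumed. These figures rest on 50 randomised per arm, a one-sided 5% test inferred from the 46 per group, the planned rates of 25% and 50%, and a refusal rate that the documents do not supply. They do not show that refusals will occur, or that they will all fall on one arm. The change is worth making because it is cheap and protects the only randomised comparison in the study.

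**What to change.** - Before allocation, confirm and record that the patient will accept either vaccine. Randomise at the vaccine visit (D0), immediately before dosing. Take the stratum from the antibody result already in hand, because a sample drawn that day would not be reported in time.
- Add to the cohort 3 criteria that the patient has not previously been randomised in cohort 2, and state that the choice between cohorts is made before randomisation.
- Define the primary cohort 2 analysis as all randomised patients by allocated arm, with a rule for missing week-4 titers, and report refusals after allocation by arm.

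The second and third items need only changes to the protocol text. The first requires both vaccines to be available at the vaccine center on the day, and someone there with access to the allocation. If same-day randomisation proves impractical, the other two still close the route into cohort 3 and fix the analysis set in advance, and randomisation should then be placed as close to dosing as the site can manage.

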Cohort 3. Our null hypothesis is that the additional homologous booster vaccine dosing with the BNT162b2 after prior BNT162b2 vaccination will increase mean titers in the spike IgG assay by at least 300%. Alternate hypothesis is that heterologous vaccination with the BNT162b2 after prior mRNA-1273 vaccination will increase mean titers by an additional 300%- that is to 600%. To achieve 80% power at a significance level alpha = 0.05, a one sided two sample t-test would require 22 samples per group to detect differences in mean titers of 750 AU/mL and 1500 AU/mL at an estimated standard deviation of 1000 AU/mL. Given we estimate 30-40% patients with have had prior mRNA-1273 vaccination and accounting for 5% dropout rate, we will thus use a planned sample size of 80.

Statistical analysis

To assess our goals as outlined above, statistical analysis will be done in the R software environment. The primary aim of cohorts 1 and 2 examining the seroconversion rates after 4 weeks will be checked with a one sample z test of proportions. The primary aim of cohort 3 examining the increase in mean Spike IgG titers will be checked with a one sided two sample t-test. Secondary aims involving the significance of associations between certain malignancies and the rates of seroconversion in our prospective single arm study will be measured by Fisher's exact and Cochran- Mantel-Haenszel tests depending on if analysis is conducted by a stratified variable (Cochran- Mantel-Haenszel) or not (Fisher's exact). The more complicated relationship between patients' seroconversion rates, their recent receipt of medical treatment, and additional factors such as history of malignancy will be examined through a multivariate logistic

regression model. After addressing the appropriateness of interaction terms, a Wald test will be used to consider the statistical significance of all included variables at the $p < 0.05$ level.

Duration

Our study will follow patients from Aug 1, 2021 through November 2023, which will allow for sufficient time to assess follow-up serologies after COVID-19 vaccination infection in patients with cancer (24 months follow up).

Matching

Cohort 1

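### Cohort 3 cannot assess switching: everyone receives BNT162b2, so the homologous versus heterologous contrast is the same variable as prior vaccine, and its objective and conclusion should be restated

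*Combined protocol and SAP*

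**What the plan says.** The Cohort 3 section of the combined protocol and SAP sets the cohort up "to address the question of whether a switch mRNA vaccine approach might be more effective at achieving an increased immune response in poor responders". On treatment it states: "Eligible patients will be prospectively followed to receive a BNT162b2 vaccine as a fourth dose". It concludes that "this cohort will allow an assessment of a switch approach in a non-randomized single arm fashion".

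The Cohort 3 primary outcome compares the 4-week rise in mean spike IgG titre after a "homologous (BNT162b2 → BNT162b2) vs. heterologous (mRNA-1273 → BNT162b2) additional booster dose of COVID vaccine". The Sample size section turns this into a hypothesis about switching: "Alternate hypothesis is that heterologous vaccination with the BNT162b2 after prior mRNA-1273 vaccination will increase mean titers by an additional 300" per cent. The Statistical analysis section specifies a one-sided two-sample t-test and states no adjustment.

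Cohort 2 patients, who meet the same antibody and prior-dose criteria, are "randomized 1:1 to receive either the BNT162b2 or AdCov2.S". Cohort 2's secondary outcomes include booster efficacy according to which mRNA vaccine was given before. The Statistical analysis section gives no method for that comparison, and nothing links cohorts 2 and 3.

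**The concern.** A switch effect is the difference between changing product and staying with the same product, with everything else equal. Cohort 3 has no mRNA-1273 patient who stays and no BNT162b2 patient who changes. The two groups differ in switch status and in the vaccine to which they responded poorly over three doses, and these two differences coincide patient by patient.

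This is not ordinary baseline imbalance. Even if the earlier vaccine had been assigned at random, the contrast would still be the sum of the two effects. A positive result could be read as support for switching when it reflects only who responds poorly to mRNA-1273 rather than to BNT162b2. A null result is just as ambiguous, since opposing effects could cancel.

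**Working it through.** **1. Reproduce the plan's figure.** Inputs from Sample size, Cohort 3: difference 1500 − 750 = 750 AU/mL, SD 1000 AU/mL, one-sided alpha 0.05, power 80%.

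n per group = 2 × (1.645 + 0.842)² × (1000/750)² ≈ 22, as stated. (The exact t-test gives 22.7, so 23, a trivial difference.) The plan adds: "Given we estimate 30-40% patients with have had prior mRNA-1273 vaccination and accounting for 5% dropout rate". At the 30% end, 22 / 0.30 / 0.95 = 77.2, so 78 patients against 80 planned. The sample size is sound for the contrast it tests.

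**2. Check whether the contrast can be split.** Cohort 3 has two cells:

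| Prior vaccine | Fourth dose | Prior mRNA-1273 | Switch |
|---|---|---|---|
| BNT162b2 | BNT162b2 | 0 | 0 |
| mRNA-1273 | BNT162b2 | 1 | 1 |

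The last two columns are identical. A design matrix with intercept, prior vaccine and switch has rank 2, not 3. Adding baseline titre or other covariates leaves the two columns identical, and so does adding patients.

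**3. Size the consequence.** Evaluable patients: 80 × 0.95 = 76. With a 30% mRNA-1273 share the groups are 22.8 and 53.2, and SE = 1000 × √(1/22.8 + 1/53.2) = 250 AU/mL. With 40% they are 30.4 and 45.6, and SE = 234. The probability of a significant result is Φ(d/SE − 1.645), where d is a shift due to prior mRNA-1273 alone, with no switch effect. The values of d are illustrative.

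| d (AU/mL) | 30% share | 40% share |
|---|---|---|
| 0 | 5% | 5% |
| 250 | 26% | 28% |
| 500 | 64% | 69% |
| 750 | 91% | 94% |

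The last row is also the test's power for a true switch effect of 750 AU/mL. The test cannot tell the two sources apart.

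**4. What cohort 2 can add.** Its BNT162b2 arm repeats the same two cells, so it adds precision to the same mixed contrast. In its Ad26.COV2.S arm both prior-vaccine groups change product. Adding that arm makes intercept, prior vaccine, Ad26.COV2.S and switch estimable (rank 4 of 4), but only if the prior-vaccine effect is the same under both study vaccines.

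The estimate is the prior-vaccine difference under BNT162b2 minus that under Ad26.COV2.S, with SE = 1000 × √(sum of 1/n over four cells). Cohort 2 has 100/2 × 0.95 = 47.5 evaluable per arm.

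- Pooled with cohort 3, 30% share: 1000 × √(1/37.05 + 1/86.45 + 1/14.25 + 1/33.25) = 373; power for 750 AU/mL is Φ(750/373 − 1.645) = 64%.
- Pooled, 40% share: SE 349, power 69%.
- Cohort 2 alone: SE 448 to 419, power 51% to 56%.

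The effect detectable with 80% power in the pooled version is 926 to 867 AU/mL, above the hypothesised 750.

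**The case against.** The plan is open about the design. It calls cohort 3 non-randomized, single arm and exploratory, and its primary outcome spells out both sequences, so a careful reader can see that the groups differ by prior vaccine. That is fair, and it makes this a matter of what is claimed rather than of anything hidden. But those labels warn of imbalance between patients. They do not say that the two effects are inseparable, and the same sections still state that the cohort assesses switching.

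A reader might infer that cohort 2 holds the missing reference groups and that the plan leaves them unused. The documents do not support this. The direct comparators for a switch between mRNA vaccines would be patients given mRNA-1273 as a fourth dose, and no cohort has any. Cohort 2 also already lists efficacy by prior vaccine type as a secondary outcome. What is missing is narrower: a specified method, and any link to cohort 3.

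A reader might also want the cross-cohort interaction to be the sole basis for a switch claim. That would replace one unverifiable assumption with another, because nothing in the documents shows that prior mRNA vaccine has the same effect on response to an mRNA booster as to an adenoviral one. Cohort 3 patients are also those who declined cohort 2, prior vaccine is not a stratification factor in cohort 2, and power falls short of 80%.

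**Conclusion.** The concern holds for cohort 3's stated objective, alternative hypothesis and conclusion: they claim something the design cannot deliver at any sample size. The aliasing follows from the text and needs no numerical assumption beyond the plan's own definition of its two groups as three doses of one product or the other.

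The size of the possible error is unknown, since the documents give no prior-vaccine effect. The probabilities above are illustrative and rest on SD 1000 AU/mL, a 30-40% mRNA-1273 share, 5% dropout and a normal approximation. They do not show that a positive result would be false, only that it would not be specific to switching.

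The figures for the optional interaction further assume that the same SD and vaccine mix hold in both cohort 2 arms, which the plan does not state.

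**What to change.** **Needed.** Keep the cohort 3 primary test and sample size. Restate the objective, hypothesis and permitted conclusion in the Cohort 3, Sample size and Statistical analysis sections, for example: *To compare the 4-week rise in mean spike IgG titre after a BNT162b2 fourth dose between patients with prior BNT162b2 and patients with prior mRNA-1273. All patients receive the same study vaccine, so a difference is not attributable to switching.* Remove or qualify the sentence saying that the cohort allows a switch approach to be assessed.

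**Optional, exploratory only.** Prespecify a prior-vaccine-by-study-vaccine interaction on the 4-week titre, adjusted for baseline titre, in cohort 2 alone and pooled with cohort 3 with a cohort term. Both study calendars already schedule spike IgG at the initial visit and D28. State beside it the equal prior-vaccine-effect assumption, that cohort 3 patients declined cohort 2, and the power for 750 AU/mL (about 64-69% pooled, 51-56% in cohort 2 alone).

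**Cost.** The needed change is wording and a more modest claim for cohort 3. The optional one is an extra model on data already planned. Neither alters treatment, visits or recruitment.
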